#### **11.7 Adverse Event Recording Period**

AEs will be monitored and recorded in study-specific case report forms (CRFs) from the time of first exposure to acupuncture.

#### **11.8 Adverse Event Reporting Requirements**

##### **11.8.1 Reporting to IRB**

The investigator will report events to the FHCRC IRB in accordance with the policies of the IRB.

## 12.0 DATA AND SAFETY MONITORING PLAN

There will be no external monitoring conducted for this study, given the low risk nature of this trial, minimal risk to participants and single institution nature of the study. The trial will be reviewed at least annually and as needed by the Consortium Data and Safety Monitoring Committee.

## 13.0 DATA MANAGEMENT/CONFIDENTIALITY

The investigator will ensure that data collected conform to all established guidelines. Each subject is assigned a unique subject number to protect subject confidentiality. Subjects will not be referred to by this number, by name, or by any other individual identifier in any publication or external presentation. The licensed medical records department, affiliated with the institution where the subject receives medical care, maintains all original inpatient and outpatient chart documents.

Subject research files are stored in a secure place, locked in the Research Coordinator's office for Urologic Oncology within the Urology Clinic at UWMC. Electronic records will be maintained in a HIPAA compliant, password-protected RedCAP database maintained by the study PI and research coordinator. Access is restricted to authorized personnel. Records will not be shared with any external personnel.

## 14.0 STATISTICAL CONSIDERATIONS

### 14.1 Study Design

This is a pilot randomized control trial. Patients who provide consent will be randomized 2:1 to receive weekly acupuncture pre-BCG treatment plus standard of care symptom management (Arm A) or to the waitlist control arm (Arm B), standard of care symptom management plus four coupons for acupuncture after study completion.

### 14.2 Primary/Secondary Endpoints/Hypotheses and Analytical Methods

#### 14.2.1 Primary Endpoint

1. Trial recruitment (proportion enrolled versus eligible, reason for not enrolling) will be described via qualitative report.
2. Trial retention (proportion retained versus all enrolled, reason for not completing) will be described via qualitative report. Successful retention is defined as continued participation within the trial until 1 week following completion of induction BCG.
3. Protocol adherence (proportion adhered versus all enrolled, specifics for how protocol was not followed and why) will be described via qualitative report. Protocol adherence is defined as completion of the acupuncture interventions and follow-up surveys if randomized to the acupuncture arm or completion of the follow-up surveys if randomized to the control arm.
4. Clinic staff's responses to surveys assessing the healthcare burden of this protocol and time spent undergoing the acupuncture therapy for the experimental arm will be described via qualitative report.
5. Adverse events associated with acupuncture therapy in the experimental arm will be described via qualitative report.

#### 14.2.2 Secondary Endpoints

1. BCG instillation adherence out of a possible planned six treatments (**successful adherence** defined as the number of successfully administered BCG instillations (of a possible 6 total)), **treatment interruptions** (defined as number of weeks that a BCG instillation was delayed), **weeks missed** (measured as any vs none, and total weeks that BCG was not administered of the planned 6 weekly induction doses of intravesical BCG), **intravesical BCG dwell times** (measured

in minutes), and **requirement for dose reductions** (measured as yes/no) between the acupuncture and control arms will be compared via t-test and chi-square as appropriate.

2. Responses of patients in the experimental and control arms to the EORTC QLQ-NMIBC-24(1) and EORTC QLQ-C30(2) symptom index will be compared via t-test at each time point.
3. **Median weekly pill counts** of medications prescribed for the management of BCG-related side effects, standardized by dosage across medication types, will be compared via Wilcoxon rank sum test.

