Population	45 BCG- adults from the UWMC Department of Urology who are scheduled to receive 6 weekly doses of intravesical BCG. Eligibility criteria includes 1) age 18 years or older, 2) English-speaking, 3) diagnosis of American Urological Association (AUA) high-risk NMIBC, including high grade (HG) pT1 (invading only the lamina propria of the bladder), recurrent HG pTa (superficial tumors), HG pTa >3cm in size or multifocal, any carcinoma in situ, any variant histology, any lymphovascular invasion, and HG prostatic urethral involvement(3) 4) have not received acupuncture in the previous 3 months, and 5) willing and able to participate in trial activities.
Primary Endpoints	
 
1. Feasibility, as assessed by recruitment, retention, and adherence to the acupuncture protocol.
 
2. Safety and tolerability of acupuncture protocol (physician reported CTCAE v5.0 adverse events).
 

[figure not shown]
Secondary Endpoints	
 
BCG treatment adherence, interruptions, dose-reductions, completion of therapy as intended
 
Patient reported urinary symptoms (EORTC QLQ-NMIBC-24) and patient-reported quality of life (EORTC-QLQ-C30)
 
Use of medications for symptom management per patient report and per prescription
 

Type of control	Waitlist arm – receives no acupuncture prior to BCG
Investigation Drug	N/A
Dose	Acupuncture: 6 weekly treatments with 30 minute needle retention
Route of administration	Acupuncture: filiform needle insertion
Regimen	6 weekly sessions treatments prior to BCG
Trial Blinding	None
Treatment Groups	Arm A: Acupuncture Intervention – Dose given pre-BCG treatment with standard of care symptom management. Arm B: Waitlist Control Arm – No dose given pre-BCG treatment with standard of care symptom management and 4 coupons for acupuncture after study completion.
Treatment Schedule	Once weekly for six weeks
Efficacy Assessments	Baseline Weekly at BCG treatment 1 week following last treatment
Number of trial subjects	45
Estimated duration of trial	12 months
Duration of Participation	Eight weeks

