Symptom management. All patients will receive standard of care medications to treat symptoms (e.g. anticholinergics such as oxybutynin, tolterodine, darifenacin, solifenacin, trospium, fesoterodine; Beta-3 adrenergic agonists such as mirabegron, local analgesics such as phenazopyridine, narcotic medications such as oxycodone if necessary, nonnarcotic medications such as Tylenol and non-steroidal anti-inflammatory medications) as indicated.

Arm B: Waitlist control arm. To minimize differences in experience between the acupuncture intervention and waitlist control arms, patients in the waitlist control arm will be escorted to the same Consultation room where the acupuncture is performed and asked to lie in a comfortable position (similar to Arm A) prior to their intravesical therapy for an identical period of time before being moved to a treatment room for intravesical instillation of BCG, according to the standard protocol detailed above. At the conclusion of the trial participants in the waitlist control arm will receive coupons to receive 4 free acupuncture appointments. All patients will receive standard of care to treat symptoms (e.g. narcotic and nonnarcotic medications, local analgesics, anticholinergic medications) as indicated.

Follow-up data collection. On a weekly basis, prior to BCG instillation and adjunctive acupuncture therapy (if applicable), patients in both the intervention and waitlist control arms will be assessed using the following metrics:

Week 1	EORTC-QLQ-NMIBC-24 EORTC-QLQ-C30 Medication Journal Assessment of complementary, alternative, and integrative therapies Acupuncture expectancy and treatment preference
Week 2	EORTC-QLQ-NMIBC-24 EORTC-QLQ-C30 CTCAE v.50 assessment of Systemic Therapy Toxicity assessing symptoms over the prior week Medication Journal
Week 3	EORTC-QLQ-NMIBC-24 EORTC-QLQ-C30 CTCAE v.50 assessment of Systemic Therapy Toxicity assessing symptoms over the prior week Medication Journal
Week 4	EORTC-QLQ-NMIBC-24 EORTC-QLQ-C30 CTCAE v.50 assessment of Systemic Therapy Toxicity assessing symptoms over the prior week Medication Journal
Week 5	EORTC-QLQ-NMIBC-24 EORTC-QLQ-C30 CTCAE v.50 assessment of Systemic Therapy Toxicity assessing symptoms over the prior week Medication Journal
Week 6	EORTC-QLQ-NMIBC-244 EORTC-QLQ-C30 CTCAE v.50 assessment of Systemic Therapy Toxicity assessing symptoms over the prior week Medication Journal
Week 7	EORTC-QLQ-NMIBC-24

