### 3.3.2 Secondary Endpoints

**Objective:** To demonstrate impact of acupuncture on BCG adherence on direct and indirect measures that include evaluation of BCG protocol experience, patient-reported outcomes of overall quality of life and urinary symptoms, and quantification of medication usage for symptom management.

Analysis plan:

1. Compare Rates of BCG instillation adherence (out of a possible planned six treatments), treatment interruptions, weeks missed, intravesical BCG dwell times (as measured in minutes), and requirement for dose reductions between the acupuncture and control arms.
2. Compare the responses of patients in the experimental and control arms to the EORTC-QLQ-NMIBC-24 symptom index, which was specifically designed to assess bladder and bowel symptoms for patients with NMIBC including assessments of impact of intravesical therapy, and the EORTC-QLQ-C30 , which assesses general quality of life. These assessments will be compared between patients by week of treatment (from week 1 to week 6).
3. Median weekly pill counts standardized by dosage across medication types will be compared between the experimental and control arms by week of therapy. Patients will be given a weekly medication diary and asked to record the number of pills/doses taken per day of specific medications which are administered for bladder symptom management while undergoing intravesical therapies. This pill diary will include topical analgesics such as phenazopyridine, anticholinergic medications, Beta-3 adrenergic receptor agonists (e.g. mirabegron), systemic pain medications including acetaminophen, nonsteroidal anti-inflammatory agents, narcotics, and other naturopathic therapies targeted at symptoms of dysuria, bladders spasms, and pelvic pain.

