**Expected results and interpretation:** We hypothesize that patients in the experimental group will have higher proportion finishing BCG regimen, with less interruptions and fewer required dose reductions of BCG. We hypothesize that patients in the experimental group will report similar general quality of life and NMIBC-specific symptoms initially. However, as patients advance in their treatments from 1 to 6 weeks, we anticipate that patients in the experimental arm will endorse improved quality of life and lower levels of bladder/bowel symptoms compared to the control arm. Furthermore, we predict that patients randomized to the experimental arm will have higher rates of protocol retention, treatment adherence, and median intravesical dwell times of the BCG at each treatment. We hypothesize that patients in the experimental arm will report taking lower amounts of adjunctive medications for bladder-related symptoms and that the discrepancy in adjunctive treatments taken will increase across the 6 weeks of therapy as the BCG-related symptoms are expected to increase with each subsequent intravesical dose of BCG.

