#### 7.5 Duration of Follow-Up

For the purposes of this study, symptom and adverse event evaluation as well as patient-reported outcomes will be collected weekly, including 1 week following completion of BCG therapy. From a bladder cancer standpoint, patients are followed on an ongoing basis, and will generally undergo a subsequent cystoscopy in clinic or the OR for the purpose bladder cancer surveillance within 2-6 weeks of completion of induction BCG to assess efficacy of the treatment and for bladder cancer response vs. persistence and/or progression. No imaging is indicated as per this protocol. However, patients with high risk NMIBC undergo annual CT scans for routine standard of care cancer staging.

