#### 14.3 Sample Size and Power

This study will have a sample size of 45 with 2:1 for treatment to control arm. The primary outcome is feasibility. This outcome is assessed through a mix of qualitative reports (trial recruitment, retention, protocol adherence, patient/provider feedback and evaluation of adverse events). For the qualitative reports there is no statistical testing, thus there is no formal power analysis. Based on prior experience we felt we needed at least 15 patients in each arm are to assess these factors quantitatively. For the patient survey, the two arms will be compared using t-test. For a trial designed with 90% power and two-sided 5% significance, we did the recommended pilot trial sample sizes per treatment arm of 15 for small standardized effect sizes (0.2) with continuous data(26). This sample size should also apply to continuous secondary endpoints. Extrapolating this reference point, we then doubled the treatment arm size in order assess some of the secondary endpoints within the treatment arm (e.g. responses of patients to the EORTC- QLQ-NMIBC-24 symptom index). Lastly, for a two-sample proportions test at 80% power and 5% significance, we calculated being able to observe a 0.4 difference between the 2 groups for binomial endpoints.

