#### 14.4 Analysis of Covariates

As this is a pilot study we do not have adequate power to adjust for covariates such as age, gender, and existing comorbidities.

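### EORTC scores are compared by unadjusted t-test although a pre-treatment score of the same scale is already collected; the weeks compared in 3.3.2 and 14.2.2 also need reconciling

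*Combined protocol and SAP*

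**What the plan says.** **Method.** Section 14.2.2(2) states that the EORTC QLQ-NMIBC-24 and QLQ-C30 "symptom index will be compared via t-test at each time point". Section 14.3 repeats it: "For the patient survey, the two arms will be compared using t-test". No section uses a pre-treatment score, whether as a covariate or through change from baseline.

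**Covariates.** Section 14.4 reads: "As this is a pilot study we do not have adequate power to adjust for covariates such as age, gender, and existing comorbidities". The pre-treatment questionnaire score is not named.

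**Pre-treatment scores.** Section 3.3 places both questionnaires in the baseline collection, before induction BCG starts. For the weekly surveys it says that, "prior to BCG instillation and adjunctive acupuncture therapy (if applicable), patients in both the intervention and waitlist control arms will be assessed". The Week 1 survey therefore also precedes any treatment.

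**Weeks compared.** Section 3.3.2(2) says: "These assessments will be compared between patients by week of treatment (from week 1 to week 6". The schedules in 3.3, 8.1 and Appendix D also collect both questionnaires at Week 7. The synopsis lists that visit among the efficacy assessments ("Weekly at BCG treatment 1 week following last treatment"), and section 7.5 says that "patient-reported outcomes will be collected weekly, including 1 week following completion of BCG therapy".

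**Expected pattern.** Section 3.3.2 states: "We hypothesize that patients in the experimental group will report similar general quality of life and NMIBC-specific symptoms initially". It then expects the arms to separate as treatment proceeds.

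**The concern.** A score taken before treatment on the same scale is often the best available predictor of the later score. Leaving it out gives up precision that costs one model term and no extra data. The reason in 14.4 does not carry over to it: a covariate that predicts the outcome reduces residual variance and raises power, while one covariate costs one degree of freedom. The control arm has only 15 patients, and the synopsis wants the secondary data to inform Phase III power calculations, so precision is scarce and of some use.

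The week range raises a separate question. Read literally, 3.3.2 compares the arms at a week when no treatment effect is possible and leaves out the scheduled score that follows the full course.

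**Working it through.** **Plan's own figures.** Section 14.3 states no power or detectable difference for the EORTC t-tests, so there is none to reproduce. Its 15 per arm is a pilot-size rule from a cited paper. Its 0.4 difference concerns binary endpoints; it reproduces (80.1% power for 0.10 against 0.50) but does not bear on this point.

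**Inputs.**
- From 14.3: 45 patients at 2:1, so 30 and 15; two-sided 5%; 80% power (the level 14.3 uses for proportions).
- Assumed: complete data, equal SD in both arms, and a pre-treatment-to-follow-up correlation ρ. The documents give none, so a range is shown.

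**Unadjusted t-test.** SE = √(1/30 + 1/15) = 0.316 SD, with 43 degrees of freedom. The non-central t multiplier for 80% power is 2.866.
- Detectable difference: 2.866 × 0.316 = 0.906 SD.
- 95% CI half-width: 2.017 × 0.316 = 0.638 SD.

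**Adjusted (ANCOVA).** The variance is multiplied by (1 − ρ²)(1 + 1/41). The second factor is the average price of estimating one covariate slope with 45 patients. Degrees of freedom are 42, the power multiplier is 2.868 and the CI multiplier 2.018. Equivalent N is 45 × (0.906 / adjusted value)².

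| ρ | Variance factor | SE (SD) | Detectable difference (SD) | 95% CI half-width (SD) | Equivalent unadjusted N |
|---|---|---|---|---|---|
| 0 | 1.024 | 0.320 | 0.918 | 0.646 | about 44 |
| 0.3 | 0.932 | 0.305 | 0.876 | 0.616 | about 48 |
| 0.5 | 0.768 | 0.277 | 0.795 | 0.559 | about 58 |
| 0.7 | 0.522 | 0.229 | 0.655 | 0.461 | about 86 |

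**Break-even.** Adjustment pays when 2.868² × (1 − ρ²)(1 + 1/41) is below 2.866², that is, when ρ exceeds about 0.16. At ρ = 0 the loss is 0.918 / 0.906 = 1.013, about 1%.

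**Weeks.** Each treatment-week survey comes before that week's instillation, so with no deferrals:
- Week 1 reflects no instillations and no acupuncture.
- Week 6 reflects five instillations.
- Week 7 reflects all six.

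Section 3.3.2 covers Weeks 1 to 6. The wording of 14.2.2 sets no limit, so with the 3.3 schedule it covers Weeks 1 to 7. The two sections do not name the same set.

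**Which survey is baseline.** Section 3.3 lists both questionnaires at baseline. The Week 0 row of 8.1 and the baseline column of Appendix D do not; both first show them at Week 1. These may be one and the same survey, but the plan does not say so.

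**The case against.** The strongest reply is that nothing here is wrong. The t-test is valid, the endpoints are secondary, the primary outcome is feasibility reported descriptively, and 14.3 promises no power for the EORTC comparisons. All of that stands, and it confines the point to an improvement in precision.

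The gain also rests on a correlation that the documents do not supply. It may be low: section 3.3.2 expects BCG-related symptoms to rise with each dose, so a score taken before BCG may predict later scores poorly. At 0.3 the gain is only about 3%. This stands too, but the downside is about 1% and the possible gain is much larger.

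The Phase III argument has limits. The synopsis does link the secondary data to later power calculations, but section 1.0 describes the later trial as aimed at treatment adherence, which adjusting EORTC scores does not affect.

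Three stronger readings are tempting, and the documents do not support them:
- A reader might infer that the unadjusted comparison is biased, or that chance baseline imbalance is a further harm. Under randomization that imbalance is already in the t-test's standard error; it is the same loss of precision, not a second one.
- A reader might infer that Week 7 is dropped from the analysis. The wording of 14.2.2 covers it, and the 3.3.2 range may simply mean the treatment weeks, with Week 7 as follow-up.
- A reader might infer that comparing Week 1 is a mistake. It can serve as a balance check, in line with the similarity expected at the start; it is just not labelled as one.

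**Conclusion.** The point holds as a low-cost improvement plus a reconciliation. A pre-treatment score is planned and unused, and the lack of power cited in 14.4 is not a reason to leave out a prognostic score of the same scale. With complete data, the detectable difference falls from 0.91 SD to 0.88, 0.79 or 0.66 SD at assumed correlations of 0.3, 0.5 or 0.7. There is no gain at about 0.16 and a loss of about 1% at zero. How much is gained in this trial cannot be settled from the documents. The primary feasibility and safety conclusions are untouched.

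Sections 3.3.2 and 14.2.2 should name the same weeks, and the baseline survey should be identified, whether or not adjustment is adopted.

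**What to change.** - **14.2.2(2) and 3.3.2(2):** at each of Weeks 2 to 7, replace the t-test with a between-arm comparison adjusted for the pre-treatment score of the same scale (ANCOVA), reported as an estimate with a 95% CI. Show Week 1 descriptively only. State that Week 7 is included. Align the t-test sentence in 14.3.
- **14.4:** state that the pre-treatment score is the one covariate adjusted for.
- **Baseline:** name the survey that supplies the covariate, and make 3.3, 8.1 and Appendix D agree. Note as a limitation that either survey may be completed after open-label allocation: 3.3 allows baseline collection at randomization or later, and Week 1 follows randomization.

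The cost is wording in these sections and one extra term per comparison. No new data are needed, since whichever survey is named is already planned. Six weekly comparisons remain, as in 3.3.2 now.

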#### 3.1.2 Secondary Objectives

To test whether acupuncture may help patients complete the 6-weekly instillations of intravesical BCG. This will be assessed through a patient's completion of BCG regimen, patient-reported outcomes of urinary symptoms and overall quality of life (as measured by the EORTC QLQ-NMIBC-24(1) and EORTC QLQ-C30(2) scales, respectively) and quantification of medication use for symptom management.

To achieve this objective, we will:

1. Compare rates of BCG treatment adherence between arms, as measured by treatment completion, treatment interruptions, and tolerance of treatment retention as measured by time retained, and dose reduction.
2. Compare patient-reported outcomes of urinary symptoms and overall quality of life between arms, as measured by the EORTC QLQ-NMIBC-24 and EORTC QLQ-C30 scales, respectively.

Quantify and compare use of medications for symptom management in patients in the intervention and waitlist control arms, as measured by medication use questionnaire.

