### **3.3 Study Design**

Baseline data collection. Prior to initiation of induction BCG, baseline data will be collected at the time of randomization, or at a subsequent baseline study visit or via the phone,email or mailing, depending on patient preference.

Baseline data collection will include 1) clinicopathologic and demographic data; 2) a patient-reported voiding and symptoms assessment using the EORTC QLQ-NMIBC-24 Survey, a validated quality of life questionnaire assessing the domains of urinary symptoms including OAB symptoms, malaise, intravesical treatment issues, future worries, bloating/flatulence, sexual function/intimacy, concerns regarding risk to partners related to therapies designed specifically for patients with NMIBC; 3) patient-reported quality of life as assessed via the EORTC-QLQ-C30 Survey, a validated generic quality of life instrument assessing the domains of depression, anxiety, physical function, pain interference, fatigue, sleep disturbance, and ability to participate in social roles and activities ranked on a 4-point Likert scale with an additional 7-point rating scale for overall health and quality of life; 4) current medication use; and 5) current use of complementary, alternative and integrative therapies 6) acupuncture expectancy and treatment preference.

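### Section 14.2.2 item 2 tests two multi-domain questionnaires week by week without naming a key score, a key week or an error rule, and plans no analysis of the pattern over time that the protocol expects

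*Combined protocol and SAP*

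**What the plan says.** Section 14.2.2 item 2 is the whole questionnaire analysis: responses in the two arms to the QLQ-NMIBC-24 and QLQ-C30 "symptom index will be compared via t-test at each time point". Section 14.3 repeats that the patient survey is compared by t-test. Section 14.4 says only that the study cannot support covariate adjustment.

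Section 3.1.2 narrows the target to "patient-reported outcomes of urinary symptoms and overall quality of life", assigning the first to the QLQ-NMIBC-24 and the second to the QLQ-C30.

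Section 3.3 describes both instruments as multi-domain. The QLQ-NMIBC-24 is described as "assessing the domains of urinary symptoms including OAB symptoms, malaise, intravesical treatment issues, future worries, bloating/flatulence, sexual function/intimacy, concerns regarding risk to partners". The QLQ-C30 is described as "assessing the domains of depression, anxiety, physical function, pain interference, fatigue, sleep disturbance, and ability to participate in social roles and activities", with a separate 7-point rating of overall health and quality of life.

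Section 3.3.2 gives the expectation. The arms are similar initially; then, "as patients advance in their treatments from 1 to 6 weeks, we anticipate that patients in the experimental arm will endorse improved quality of life". It also expects fewer symptoms in that arm.

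The time points differ between sections. Section 3.3.2 item 2 compares weeks 1 to 6. The Section 3.3 schedule, Section 7.5 and Appendix D also collect Week 7. Section 3.3 places each weekly assessment before that day's acupuncture and BCG.

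**The concern.** The plan is written as significance testing, but it does not fix what is tested. Which score counts, at which week and at what error rate are all open, and the questionnaire comparisons are not labelled exploratory. Those choices could be made after the data are seen.

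The tests also do not match the hypothesis. Arms that start alike and then separate form an arm-by-time pattern. Separate weekly t-tests can display it but do not test it, and they ignore that the same patients are measured each week. One of the tests, at Week 1, cannot show a treatment effect because no treatment has been given.

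The stake is limited but real. The Synopsis says the secondary data will inform power calculations for a Phase III trial. An effect picked because its domain and week crossed 5% tends to be too large, and a later trial sized on it would be too small.

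**Working it through.** **The plan's own figures.** The documents give no number of questionnaire tests and no family-wise error rate, so there is no figure on this point to reproduce. The nearest is the 0.4 difference in proportions in Section 14.3. With 15 control and 30 acupuncture patients at two-sided 5%, 0.10 vs 0.50 gives 80.1% power. For control rates of 0.05 to 0.50 the detectable difference is 0.375 to 0.43. The 0.4 therefore reproduces, subject to the unstated base rate.

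**Inputs.**
- Arms: "This study will have a sample size of 45 with 2:1 for treatment to control arm" (Section 14.3), so 30 and 15.
- Level: 5% two-sided per test. This is an assumption, taken from "For a trial designed with 90% power and two-sided 5% significance" in Section 14.3; Section 14.2.2 states no level.
- Scores: 7 domains for the QLQ-NMIBC-24, 7 for the QLQ-C30, plus 1 global rating (Section 3.3), so 15; or 2 if each questionnaire yields one score.
- Weeks: 6 (weeks 1 to 6, Section 3.3.2), 7 (all collected weeks), or 5 (weeks 2 to 6, leaving out the pre-treatment Week 1). Weeks 2 to 7 also make 6.
- Correlations between scores and between weeks: not in the documents, so a range is shown. No missing data assumed.

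**Number of tests = scores × weeks; expected false positives = 0.05 × tests.**
- 15 × 5 = 75, expected 3.75
- 15 × 6 = 90, expected 4.5
- 15 × 7 = 105, expected 5.25
- 2 × 6 = 12, expected 0.6
- 2 × 7 = 14, expected 0.7

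(One score per questionnaire over weeks 2 to 6 only would be 2 × 5 = 10, expected 0.5.) The expected counts do not depend on correlation.

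**Chance of at least one false positive.** If independent, 1 − 0.95^k: 1 − 0.95^90 = 99.0%, 1 − 0.95^12 = 46.0%, 1 − 0.95^14 = 51.2%. Scores from the same patients are likely to be positively correlated, so null trials (30 vs 15, pooled t-test, 4,000 per setting) were simulated:

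| Correlation between scores / between weeks | 90 tests | 12 tests | 14 tests |
|---|---|---|---|
| 0.2 / 0.4 | 96.9% | 41.6% | 44.4% |
| 0.3 / 0.5 | 93.9% | 36.2% | 40.7% |
| 0.3 / 0.7 | 88.4% | 29.0% | 32.6% |
| 0.5 / 0.7 | 80.0% | 28.9% | 30.1% |
| 0.6 / 0.8 | 65.0% | 25.2% | 25.5% |
| 0.7 / 0.9 | 50.0% | 17.4% | 18.8% |

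With no correlation between scores and 0.6 between weeks, the figure for 90 tests is 96%. For 90 tests the working range is therefore about 50% to 96%, approaching 99% only as correlation vanishes. For 12 to 14 tests it is about 17% to 44% with correlation and up to 51% without.

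**Timing, side by side.** Each questionnaire precedes that visit's treatment. The Week 1 score therefore follows no sessions, the Week 6 score follows five, and only the Week 7 score follows all six. The weeks 1 to 6 window in Section 3.3.2 includes the one comparison that cannot show an effect and omits the one that reflects the full course.

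**With the target named.** One test has 5% error. Two unadjusted independent tests have 1 − 0.95² = 9.75%; at 2.5% each the total is held at 5%. For a plain 30 vs 15 t-test, 80% power needs a difference of 0.91 SD at 5%, or 1.01 SD at 2.5%. At 0.8 SD, an assumed value, power is about 70% and 58% respectively; at 0.5 SD it is 34% and 24%.

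**The case against.** The strongest reply is that this is a feasibility pilot. Its primary outcome has no statistical testing, its secondary data are meant to inform a later trial, and no section makes Phase III depend on a p-value. That stands, and it limits the severity. It does not remove the point, because the plan still specifies significance tests and does not call them exploratory.

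Four stronger readings are tempting, and the documents do not support them.

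- A reader might infer that a chance finding is near certain. That needs nearly independent tests; with plausible correlation the figure can fall to about 50%.
- A reader might take 90 tests as the plan's number. The 15 scores come from a description of the instruments under baseline data collection, not from the analysis section. Section 14.2.2 speaks of a symptom index in the singular, which can mean one score per questionnaire. The documents do not settle it.
- A reader might say that no target is named at all. Section 3.1.2 does name the two constructs; Section 14.2.2 fails to carry them through to a score and a week.
- A reader might say that a gap growing week by week is hypothesised for the questionnaires. Section 3.3.2 words an increasing discrepancy only for medication use. For the questionnaires it says similar at first, then better.

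It is also fair to object that a repeated-measures model is not bound to gain power. The gain depends on an effect size and a correlation that the documents do not give. In simulations with a difference growing linearly to 0.8 SD at Week 7, a trend test had between 49% power (strong serial correlation) and 92% (exchangeable correlation of 0.6). The case for the change rests on fixing the target in advance, not on power.

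**Conclusion.** The point holds as an under-specified analysis of secondary endpoints that should be corrected. Section 14.2.2 item 2 leaves the score, the week and the error rule open, and no planned analysis addresses the expected pattern over time. The size depends on a reading that the plan does not settle: 75 to 105 tests if each score is tested (for 90 tests, 4.5 expected false positives and about a 50% to 96% chance of at least one), or 12 to 14 if each questionnaire gives one score (about 17% to 51%). These figures assume 5% two-sided per test, 30 and 15 patients with complete data, and the correlations shown. Three findings need no assumption: the Week 1 test is a baseline comparison, Section 3.3.2 and the collection schedule disagree on Week 7, and no multiplicity rule or analysis over time is stated.

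**What to change.** In Section 14.2.2 item 2:

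1. Name two key scores that match Section 3.1.2: the urinary-symptoms scale of the QLQ-NMIBC-24 and the overall health and quality-of-life score of the QLQ-C30.
2. Fit one repeated-measures model per score, with arm, week and arm-by-week, and patient as the repeated unit. Use the pre-treatment Week 1 score as baseline, not as an outcome. Section 14.4 should then say that its statement on covariates does not rule out the baseline score.
3. Name one contrast: the arm difference one week after the last instillation. Amend Section 3.3.2 item 2 to include Week 7.
4. State the error rule: either 2.5% for each of the two tests, or that both are exploratory at 5%.
5. Report the arm-by-week trend as supportive, and all other domains and weeks as estimates with 95% confidence intervals and no significance claims.

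If power is quoted for these contrasts, give it as a range over the assumed effect and correlation, or leave it out.

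The cost is a wording change and two models in place of many t-tests. No extra patients, visits or data are needed. The downside is that the other domains become descriptive, and splitting the error raises the difference detectable with 80% power by a plain t-test from 0.91 to 1.01 SD.
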